8.2.4.3 Genetic counseling - Not applicable

8.3 SAFETY AND OTHER ASSESSMENTS

- Biological specimen collection and laboratory evaluations.
For metabolic analysis, blood samples will be drawn at screening visit (basic metabolic panel), baseline (admission pre-intervention) and at discharge (admission post-intervention), as per Section. Additionally, blood will be drawn for beta-OHB levels at defined intervals (see Section 1.3 Schedule of Activities for details)
- Special assays or procedures required - continuous glucose monitoring
- No storage of specimen required. The data will be downloaded from the sensor attached to skin of the back of the upper arm to the Reader twice, on admission and on discharge.
- Heart rate variability monitor
- No storage of specimen involved. Data will be stored on a central application
- Counseling procedures, including any dietary or activity considerations
Counseling will occur at study debriefing visit on day of discharge or as otherwise arranged, and may also occur at any point during the one-week admission (Visit #2) or during the screening visit (#1). Counseling will be primarily focused on healthy diet, including low glycemic index, DASH diet, and Mediterranean diet as per USDA guidelines, and will emphasize that ketogenic diet remains a matter of research interest regarding previously found / putative benefits for Parkinson's Disease, however is congruent with aspects that are recommended by dietitians and physicians, such as minimizing salt and high glycemic index refined carbohydrates.
- Assessment of study intervention adherence - see Study Intervention Compliance, section 6.4
Administration of questionnaires or other instruments
At screening visit (#1), participant will be asked to fill out PDQ39, and UPDRS (Parts 1, 2 and 4) and NMSS will be administered by PI. On the day of discharge, UPDRS and NMSS will be repeated.
- Assessment of adverse events.

There will be daily monitoring performed by metabolic unit staff and communicated to PI if concern, in turn discussing with independent medical monitor (IMM) and possibly unblinding AI if additional care required such as stopping the intervention, transfer to ICU. There will be no modification to the diets as outlined, to facilitate maintaining blinding and primary and secondary objectives of feasibility and ketosis ascertainment, respectively. There will be weekly meetings by investigators if any adverse events occurred as per Policy 801 (Refer to Section 8.4 for descriptions).

Abbreviated Title: Tolerability and efficacy of ketogenic diet in Parkinson's Disease

Version Date: 04/19/2021

Intervention side effects will be identified by the study LIP who is monitoring the patient during the admission and has daily contact with the participant. With blood glucose monitoring during the study, the nurses will contact study investigators for blood glucose value < 70 mg/dL. The hospital protocols are triggered for BG <40mg/dL that involve sending sample to NIH CC lab, including contacting study investigators for emergent care. For blood glucose 40-70, there will be the following procedure: if asymptomatic and fully alert, 1 cup juice / crackers, recheck in 30 minutes, repeat as necessary. If symptomatic (such as light-headedness, headache, nausea) / mental status lethargy, provide juice / crackers and contact study investigators for possible IV D50 administration.

The literature on safety of the ketogenic diet in adults in clinical trials is robust, including several trials in Parkinson's disease (Krikorian et al 2019, Phillips et al 2018, Vanitallie et al 2005) . The majority of these trials were conducted in the outpatient setting and adverse events were quite rare and typically minor in severity. Similarly, MCT powder/oil as a supplement to accelerate ketogenesis is reported to be safe in Alzheimer's Disease patients (Reger et al, 2004) as well as healthy volunteers (Harvey et al, 2018). Participants will be provided with contact information for the study team and asked to report any concerns, problems or new symptoms. During the 2-week outpatient phase, telephone monitoring may also occur as needed.

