1.3 SCHEDULE OF ACTIVITIES (SOA)

Procedures	Screening/ enrollment *	Day 1 (pre- intervention)	Day 2 (diet started)	D 3	D 4	D 5	D 6	D 7	W 3 (post)
Fill out intake form and determine eligibility	X								
Pregnancy test**	X								
Informed consent	X								
Randomization to Ketogenic Diet or Usual Diet group, stratified 2-factor covariate	X								
anthropomorphic measures (height, weight, abdominal circumference)	X							X	X
Vital signs, including orthostatic (exploratory outcome)	X	X	X	X	X	X	X	X	X
History and Physical Exam	X	X							
Focused Neurologic Exam	X	X							X
Bioelectric Impedance (BIA)	X								X
MOCA	X								
Screening BMP (to establish eGFR), hepatic panel, lipid panel, A1C, beta-HCG if female < age 60	X								

Abbreviated Title: Tolerability and efficacy of ketogenic diet in Parkinson's Disease

Version Date: 04/19/2021

Procedures	Screening	Day 1	Day 2	Day 3	Day 4	Day 5	Day 6	Day 7 / Post	W 3 (post)
UPDRS part 3	X	X	X	X	X	X	X	X	X
Total UPDRS	X								X
Hoehn & Yahr Stage	X								
Electrocardiogram (ECG)	X*	*(If ECG service is unable during screening, may be performed on Day 1 prior to initiation of diet)							
metabolic labs (A1c, insulin, CRP, apolipoprotein panel, HOMA-IR, cortisol, TSH, T3, free T4), BDNF (exploratory outcome), lipid panel (day 7, week 3), A1c (week 3 only)		X						X	X
Non Motor Severity Scale (NMSS) (exploratory outcome)	X								X
PDQ-39 questionnaire (exploratory outcome)	X								X
Resting heart rate variability (2-10 min)		X	X	X	X	X	X	X	X

Abbreviated Title: Tolerability and efficacy of ketogenic diet in Parkinson's Disease

Version Date: 04/19/2021

Procedures	Screening	Day 1	Day 2	Day 3	Day 4	Day 5	Day 6	Day 7 / Post	W 3 (post)
(exploratory outcome)									
Cardiovascular testing – Valsalva maneuver, deep breathing (exploratory outcome)		X						X	X
Timed up and Go (TUG) AM fasting (secondary outcome)	X	X	X	X	X	X	X	X	X
Simple reaction time (SRT) daily (exploratory outcome)		X	X	X	X	X	X	X	X
9-hole pegboard test (9-HPT) daily (exploratory outcome)		X	X	X	X	X	X	X	X
daily journal of ON/OFF and keto-induction symptoms, (Likert scales) and mood (exploratory outcome)		X	X	X	X	X	X	X	X
EEG spectral analysis and connectivity analysis (phase lag index) days 1, 7 (exploratory outcome)		X						X	X
Respiratory Metabolic Cart quotient (pCO ₂ , :pO ₂) for resting and energy expenditure	X								X
BMP, magnesium		X		X	X	X	X	***	

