3. OBJECTIVES AND ENDPOINTS

OBJECTIVES	OUTCOME MEASURES	JUSTIFICATION FOR ENDPOINTS
Primary		
Feasibility of MCT-KD x three weeks	Composite outcome (all of the following measures must be met):	MCT-KD has never been studied in PD population (expected to

Abbreviated Title: Tolerability and efficacy of ketogenic diet in Parkinson's Disease**Version Date:** 04/19/2021

	
1) Recruitment reaches target of 32 participants or as per pre-set interim analysis
 
2) Study retention rate >80% of all participants at 3 weeks
 
3) Adherence ($\leq 10\%$ mean daily energy from net carb over 2 weeks MCT-KD outpatient, assessed by 2x/week unscheduled phone calls by CC Nutrition staff)
 
4) Acceptability – Likert scale ≥ 2 (at least somewhat likely to use diet in future and at least somewhat effective in improving PD symptoms) at end of study (week 3)
	augment ketosis) and feasibility has not been established.
Secondary		
Timed Up & Go (TUG) time, mean difference between groups on study day 7	Mobility on the Timed Up and Go (TUG) test, daily (fastest of three trials per session) units: seconds Range: 8-18s	TUG time is generally regarded as an index of fall risk – estimated 20% risk reduction with 4s faster time (Nocera et al, 2013)
Tertiary/Exploratory		

Nutritional ketosis (NK) improves PD symptomatology at three weeks in the following: in cognition (improved attention, recall, and executive function), and motor function (reduced akinesia and tremor). A low fat (standard American) diet (SAD) does not.
 
NK reduces non-motor symptoms, subjective motor fluctuations and daily off time within the immediate keto-induction period, while SAD does not (mean difference at 1
	
Stroop word-color interference latency (unit: ms, range: 110-135 ms), 0,1,2,3 back recall task (unit i: % error of missing true n-back letter presented; range i: 0-back 0-10%, 1-back 4-20%, 2-back 15-30%, 3-back 20-32%; unit ii reaction time (RT) ms, range ii 0-back 500-740 ms; 1-back 600-980 ms; 2-back 700-1200 ms; 3-back 700-1200 ms); fingertap speed and rhythm (MN and PQ keyboard tasks; units MN and PQ keystroke speed, in keys/s; range MN
	
All of these tests have been shown to be impaired in PD cohorts and are at least semi-quantitative and amenable to serially repeated measures with good test-retest reliability
 
Scalp EEG is non-invasive, easy to perform in the setting of intervention, and as

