The interventional food-based product, Liquigen® (KetoCal), will be administered by NIH CC Nutrition staff to MCT-KD group participants as per defined blinded diet.

Primary Outcome: feasibility will be assessed in a composite fashion by retention rate >80% at study end (week 3) ; study adherence in the outpatient segment defined by maintaining mean carbohydrate limit ≤ 10%, as by CC nutrition staff twice weekly unscheduled calls data input to online application); reaching recruitment target of 32 participants, unless otherwise defined by interim analysis (see Section 9); and acceptability by likelihood to use the diet in the future and effectiveness in reducing PD symptoms both “somewhat” ≥ 2/4 on Likert scales. All criteria must be met.

Secondary outcome: Timed Up & Go (TUG) time at between MCT-KD and SAD groups mean difference on inpatient day 7.

Exploratory outcomes:

Effort will be taken in establishing medication and testing schedules, for outcomes to be assessed at the same time from last dopaminergic medications and other psychotropic medication administrations including cholinergic and muscle relaxants (see table 2). All exploratory outcomes will be assessed pre (admission day 1) and post (day 7 and week 3) diet intervention. Additionally, reaction time, Stroop test, N-back test, MN/PQ fingertapping tests, 9-HPT, UPDRS-3, and resting HRV will be tested daily on admission days 2-6.

Stroop word color interference latency (Stroop test B), N-back test (3-back letter), MN and PQ keystroke tasks, tremor accelerometry, 9-hole pegboard test (9-HPT), and simple reaction time (SRT), EEG waveform analysis (steepness ratio, sharpness ratio, modulation index), and quantitative (q)EEG assessment; daily assessments of heart rate variability (SDNN, pNN50, rMSSD, power spectral analysis), and supine to standing blood pressure and heart; resting heart rate (5 min recordings daily), UPDRS including daily UPDRS-3, daily ON time, daily PD symptoms, daily keto-induction symptoms, pre vs. post intervention Non-Motor Symptom Severity Score (NMSS)

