As per pre-determined scheduled time, subjects will receive monitoring daily on study days 1-7 for 5 minutes using Elite HRV finger monitor and Android application in relaxed waking state in the reclined seated position. Additionally, on study days 1, 7, and week 3 (pre/post intervention), at the time of sessions with rsEEG (see table 2 for testing schedule), trials of Valsalva Maneuver (VM) and deep breathing (DB) will be conducted as follows: VM with coaching to blow into mouthpiece attached to manometer to pressure of 40 mmHg x 15 seconds, and the recording of heart rate cardiovagal gain over the subsequent 1 minute (max RR / min RR interval); average of 3 trials will be used for analysis. DB will occur for 1 minute with 6 cycles per minute, average of 2 trials. Recording for cardiovagal testing will be conducted study day 1, 7, and week 3 via ECG electrodes using Natus Neurology machine (not FDA approved). Analysis will be done using EliteHRV and Biopac Acqknowledge software to extract using artifact removed R-R wave (N-N) intervals SDNN, pNN50, rMSSD, and power spectral analysis (LF, HF, VLF, LF/HF ratio).

Orthostatic vital signs

Orthostatic blood pressure and heart rate will be recorded daily, study days 1-7 and week 3 - supine for 10 minutes or more, then standing immediate followed by standing at 3 minutes.

UPDR parts 1, 2, and 4 will be tested pre vs. post intervention (day 1, week 3). UPDRS-3 will be assessed daily, similar time each day and relation to medications in ON state, with video recording. UPDRS-3 measures to be assessed by board certified neurologist, either directly by AI or rated by blinded rater not affiliated with the study

Abbreviated Title: Tolerability and efficacy of ketogenic diet in Parkinson's Disease

Version Date: 04/19/2021

ON-time, PD symptoms, and keto-induction symptoms will be captured daily via online survey provided / collected to participant daily to check PD / keto symptoms and daily waking hours in the "off" state without effect of dopaminergic medications. Psytoolkit URL:

<https://www.psytoolkit.org/c/3.0.0/survey?s=RQFaX>

Pre vs. post intervention non-motor symptom severity scale (NMSS, Chaudhuri et al 2007, validated by MDS) will be tested for presence/absence of fatigue, pain, urinary disturbance, and other non-motor symptoms (day 1, week 3).

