8.2.1 Clinical Evaluations

Physical examination

Participants will be examined at screening visit by board certified neurologist and movement disorder specialist with focused examination:

general, cardiopulmonary auscultation, neurologic exam with focus on motor or other system disorders (such as sensory, musculoskeletal) related to Parkinson's. There will also be UPDRS and request for video recording. Video record would require separate signed informed consent as per NIH protocol. Video recording is done for research purpose only (quality assessment by averaging scores of in-person rater with a separately blinded video rater).

Examination with requested video recording as per above will be repeated on day of discharge (post-intervention). Examination as per above will also be repeated on day of admission (pre-intervention), without request for video recording unless a significant clinical finding is observed in difference from the screening visit.

Vital signs and Heart rate variability

Vital signs will be done as per routine care in the Metabolic Unit and will also include daily orthostatic check to be done by Metabolic Unit staff or credentialed study investigator. Daily heart rate variability will be performed with pre/post intervention (daily days 1-7 and at week 3) heart rate responses to a) deep breathing at 6 cycles per minute (5 cycles E:I ratio) and difference between average max and min heart rates; and b) Valsalva Ratio (HR max : HR baseline) with Valsalva Maneuver x 15s at 30-40 mmHg (days 1, 7, and week 3).

Radiographic or other imaging assessments

ECG – ECG will be performed at screening or Day 1 of admission (depending on availability), however must be performed prior to diet intervention. A routine ECG will be performed for confirmation of normal cardiopulmonary function. If arrhythmia is detected, Cardiology will be consulted and incorporating their recommendations, decision about remaining or withdrawing from the study based upon the underlying etiology sinus (more likely stay in the study) vs. non-sinus rhythm aberrancy (more likely withdraw from study) as per inclusion/exclusion criteria.

EEG - regional changes in spectral power (theta, alpha, beta) and nonlinear corticocortical synchronization measure via phase lag index (focusing on frontotemporal, parietotemporaloccipital areas

Abbreviated Title: Tolerability and efficacy of ketogenic diet in Parkinson's Disease

Version Date: 04/19/2021

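### The protocol conflicts on whether NMSS and total UPDRS are measured at day 7; if the schedule is followed, these scales give no randomised comparison for the one-week non-motor hypothesis

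*Combined protocol and SAP*

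**What the plan says.** **The hypothesis.** The exploratory part of the Section 3 table states: "NK reduces non-motor symptoms, subjective motor fluctuations and daily off time within the immediate keto-induction period, while SAD does not (mean difference at 1"; the sentence ends by giving one week as the time point. NMSS is among the outcome measures listed there.

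**Text that omits day 7.** In Section 1.3 the row "Non Motor Severity Scale (NMSS) (exploratory outcome" is marked at screening and week 3, and the total UPDRS row is marked the same way. UPDRS part 3 has its own row, marked at screening, on every inpatient day and at week 3, so the gap concerns parts 1, 2 and 4. Section 4.1, describing the individual tests, says "UPDR parts 1, 2, and 4 will be tested pre vs. post intervention (day 1, week 3" and dates the NMSS assessment of fatigue, pain, urinary disturbance "and other non-motor symptoms (day 1, week 3".

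**Text that includes day 7.** Earlier in Section 4.1 the rule is: "All exploratory outcomes will be assessed pre (admission day 1) and post (day 7 and week 3) diet intervention". The list that follows names UPDRS and NMSS. Section 8.3, after placing UPDRS parts 1, 2 and 4 and NMSS at screening, adds: "On the day of discharge, UPDRS and NMSS will be repeated". The synopsis equates the end of admission with day 7. Section 8.2.1 says of the screening examination, which includes UPDRS: "Examination with requested video recording as per above will be repeated on day of discharge (post-intervention".

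**Which text governs.** The synopsis says that between-group comparisons at day 7 and over days 1 to 7 apply to most outcomes but not all, and refers the reader to Section 1.3 for which ones.

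**The concern.** The hypothesis contrasts two diets, so it needs a time when the arms are on different diets. That holds only during the inpatient week; afterwards everyone is on the ketogenic diet at home. A site working from the schedule of activities, as sites normally do, would record no NMSS and no UPDRS parts 1, 2 or 4 at discharge. Those values cannot be recovered once the SAD arm starts the ketogenic diet.

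The gap falls where the protocol reports the earlier signal. Section 2.1 describes the UPDRS reductions in the earlier ketogenic pilots as larger for non-motor than for motor scores. Section 2.3.2 reports the greatest improvement in UPDRS part 1 in the larger of those trials. Section 2.1 also criticises one pilot for having no control group and no blinding. A week-3 NMSS with no non-ketogenic control, after two weeks of a diet that participants know to be ketogenic, would share much of that weakness.

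**Working it through.** No figure in the plan is in dispute, so the check is to set the texts side by side.

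| Source | Baseline | Day 7 / discharge | Week 3 |
|---|---|---|---|
| 1.3, NMSS and total UPDRS rows | Screening | No | Yes |
| 4.1, text on individual tests | Day 1 | No | Yes |
| 4.1, general rule for exploratory outcomes | Day 1 | Yes | Yes |
| 8.3, questionnaires | Screening | Yes | Not stated |
| 8.2.1, examination including UPDRS | Screening, repeated at admission | Yes, parts not specified | Not stated |
| 9.1, list for day 1, day 7 and week 3 | NMSS and total UPDRS not listed | Not listed | Not listed |

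**Step 1: ketogenic exposure at each visit.** The synopsis gives 6 days of randomised diet, then 2 weeks of ketogenic diet for all.

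- Day 7: MCT-KD arm up to 6 days; SAD arm 0 days.
- Week 3: MCT-KD arm 6 + 14 = 20 days; SAD arm 0 + 14 = 14 days.

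The week-3 contrast is therefore about 3 against 2 weeks of the same diet. It does not estimate ketosis against SAD.

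**Step 2: what can be tested at one week under each version.**

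- Under Section 1.3 and the test-by-test text of Section 4.1, there is no day-7 value and so no ketosis-versus-SAD contrast on NMSS or UPDRS parts 1, 2 and 4.
- Under the general rule of Section 4.1 and Section 8.3, there is a day-7 value and the contrast can be tested.
- UPDRS part 3 is daily in Section 1.3 and can be compared between arms at day 7.

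**Step 3: size of the comparison at stake.** Section 9.2 plans 32 participants, 16 per arm, with 14 per arm needed after the allowance for dropout. So the number is nominally 16 against 16 before any loss.

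**Step 4: baseline.** Section 9.4.3 adjusts each exploratory outcome for age and its day-1 value. The schedule has no day-1 NMSS or total UPDRS; it has screening values. Even with a day-7 column added, the ANCOVA could not be run as written on data collected to the schedule.

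**Step 5: what else is available at day 7.** Section 1.3 places the Geriatric Depression Scale (GDS) and the Gastrointestinal Symptom Rating Scale (GSRS) at day 7. The ON/OFF, symptom and mood journal is kept daily in both arms.

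**The case against.** The strongest case on the other side is that the authors meant NMSS and total UPDRS as before-and-after measures only. The synopsis labels both as pre versus post, it warns that not every outcome has a day-7 group comparison, the Section 9.1 list for day 1, day 7 and week 3 includes GDS but not NMSS, and exploratory Hypotheses A and B do not name NMSS. On that view, correcting Section 8.3 to match the schedule would resolve the conflict equally well. The one-week hypothesis also covers motor fluctuations and off time, which the daily survey records, and GDS is itself described as validated. Nothing here enters the feasibility composite, the Timed Up & Go (TUG) endpoint, the sample size or the interim analysis.

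Much of this stands. The outcomes are exploratory, and one-week comparisons on other measures remain possible. It does not remove the conflict. Section 3 lists NMSS among the outcomes for objectives that include a one-week between-diet claim, and the synopsis places its pre-versus-post comparisons at both 1 and 3 weeks. The substitutes are also partial: GDS covers depression, GSRS covers gastrointestinal symptoms, UPDRS part 3 is motor, and Section 8.2.3 says the Parkinson items of the daily survey come from the investigators' clinical experience.

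A reader might go further and infer that the plan schedules these scales at screening and week 3 alone, so that the non-motor hypothesis cannot be tested and the randomised comparison is lost entirely. The documents do not support that. Section 8.3 places both scales at discharge, and the general rule in Section 4.1 places them at day 7. The loss occurs only if the schedule prevails.

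**Conclusion.** The point holds as an internal contradiction with a conditional consequence. Section 1.3 and part of Section 4.1 omit day 7 for NMSS and UPDRS parts 1, 2 and 4; the general rule in Section 4.1 and Section 8.3 include it. The baseline visit conflicts as well.

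If staff follow the schedule, the nominal 16-versus-16 comparison at one week is not collected on these scales, and the week-3 data contrast only about 20 with 14 days of ketogenic diet. If they follow Section 8.3, the comparison exists, but the covariate in Section 9.4.3 still has no matching visit in the schedule. The conditional part rests on one assumption: that the schedule governs in practice. The synopsis makes this plausible by deferring to Section 1.3, but the documents do not settle it.

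The primary feasibility conclusion and the secondary TUG conclusion are unaffected. The point is worth correcting because the protocol states the hypothesis, already promises the assessment in one place, and has only one opportunity per participant to collect it.

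**What to change.** - In Section 1.3, mark NMSS and total UPDRS in the day-7 column, as Section 8.3 already states.
- Align the test-by-test text of Section 4.1 and the outcome list in Section 9.1 with that, and state in Section 8.3 that the week-3 assessment is also done.
- Name one baseline visit, screening or day 1, for these scales throughout, and make the Section 9.4.3 covariate refer to that visit.
- State in Section 9.4.3 that the day-7 ANCOVA between arms is the analysis for the one-week non-motor hypothesis in Section 3, and that week-3 values are read without a SAD control.

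The cost is one short questionnaire session per participant on day 7, at most 32 in all, on a day that already carries EEG and autonomic testing, plus wording changes. If day 1 is chosen as baseline, a day-1 session is added too; choosing screening avoids this.

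If the sponsor does intend these scales as before-and-after measures only, the conflict can instead be removed by amending Section 8.3 and the general rule in Section 4.1. Section 3 should then name the measures that carry the one-week hypothesis. That gives up the controlled comparison on NMSS and UPDRS parts 1, 2 and 4, so it is the weaker choice.
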